At our institution, all patients scheduled to undergo total knee replacement spinal anesthesia as well as infiltration of local anesthetic into the Interspace between the Popliteal Artery and posterior Capsule of the Knee (IPACK) injections as part of their pain management, as this practice provides analgesia while preserving motor function.(5)¹ Postoperatively, all patients receive adductor canal peripheral nerve catheters.

We hypothesize that the combination of ultrasound-guided adductor canal nerve catheter, IPACK block, and single injection genicular nerve blockade will further decrease opioid consumption and pain scores, therefore leading to decreased systemic side effects and improved overall satisfaction compared to ultrasound-guided adductor canal catheter and IPACK block alone in patients undergoing elective minimally invasive TKA surgery.

4. Design and Procedures

This is a single center, prospective, randomized, controlled, single-blinded study. 40 subjects will be recruited (see #6 Recruitment and Compensation below), 20 in each group.

Primary Outcome:

Cumulative opioid consumption at 24 hours.

Secondary Outcomes:

- Quality of analgesia at rest and with movement, as measured by numerical pain rating scores (NRS-11) up to 48 hours (0h, 6h, 24h, 36h, 48h)
- Cumulative opioid consumption at 48 hours
- Opioid consumption and quality of analgesia based on patient diary after discharge on postoperative day 7 (worst pain score)
- Sleep quality based on number of times awakened on the evening of POD#0
- Subject satisfaction with the block technique at 24h and POD#7
- 20 meter walk test time on POD#1. This will be conducted on 6100, the orthopedic floor. Research staff will conduct the test, which will involve the patient walking at his/her fastest pace to a mark on the floor 10m away, then turning around and returning to the start line.

Preoperative Management

Subjects will be randomized on the morning of surgery to receive either genicular nerve blocks using 15mL 0.25% bupivacaine with 2mg dexamethasone or the same blocks with 15 ml of saline.

Prior to the block in the preoperative holding area, all subjects will receive the standard oral multimodal analgesic regimen, a spinal anesthetic with 12.5 mg of bupivacaine, and posterior capsule infiltration with 20 ml of 0.2% ropivacaine. Subjects will then receive the study intervention.

Single injection genicular nerve block technique

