Subjects will receive a spinal anesthetic using intravenous propofol infusion for sedation. No muscle relaxation will be permitted. In addition, no long-acting opioids will be administered for analgesia; instead, boluses of fentanyl 25 to 50 mcg will be administered as guided by respiratory parameters and/or hemodynamics. Subjects will maintain spontaneous ventilation throughout surgery. Respiratory rate greater than 18 per minute will be treated by administration of 25 to 50 mcg of fentanyl. At the conclusion of the case, the propofol will be discontinued and the subject awakened. Subjects will be transported to PACU. All subjects will receive intravenous fentanyl and/or oral oxycodone as needed for pain management.

Postoperative Evaluation

Evaluation of both pain intensity (NRS-11 pain scale) and interval opioid consumption will be undertaken at the following time points in a blinded fashion by a member of the research team:

- PACU (30-60 minutes after arrival to PACU)
- 6 hours postoperatively
- 24 hours postoperatively

- 36 hours postoperatively
- 48 hours postoperatively
- POD 7 (morning of POD#7)

All data will be recorded in a REDCap database. Subjects will be provided with a diary to record the relevant data elements. Calls will be made on POD 7 to record the data in the research record by a member of the research team.

Sleep quality will also be assessed by a member of the research team on POD#1 as a function of the number of times the patient was awoken by pain.

Occurrences of adverse events reported by subjects will also be collected during the phone interview on POD#7. Subjects will be queried as to any block related complications (e.g., prolonged motor blockade or numbness) and opioid-related adverse events. Satisfaction with the postoperative pain management experience will also be graded on a 0-10 point scale on POD#7.

5. Selection of subjects

Criteria for inclusion:

- Subjects scheduled for primary elective total knee arthroplasty
- Age 56-85 years of age
- American Society of Anesthesiologists Physical Status I-III
- BMI 18-40 kg/m²

Criteria for exclusion:

- Inability to cooperate with protocol
- Inability to understand or speak English
- Allergy to ropivacaine, bupivacaine or other local anesthetic
- Contraindication to peripheral nerve block (e.g. local infection, neurologic deficit or disorder, previous trauma or surgery to ipsilateral knee, etc.)
- Revision knee surgery

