There will be no costs to the subject for participation in the study. Subjects will not be compensated for their participation.

12. Data analysis and statistical considerations

Based on our institutional experience with primary total knee arthroplasty and postoperative opioid consumption, we calculate that 20 patients per group (total of 40) will be required to detect a 30% difference in our primary outcome measure.

Baseline patient demographic and clinical characteristics as well as surgical factors will be compared between treatment groups. The difference in the primary outcome, 24h

opioid consumption, will be assessed via two-sided two-sample t-test. Outcome data distribution will be assessed for normality and log-transformed if necessary. If differences in key patient factors are identified between groups we will pursue a multivariable linear model in order to control for potential confounding of treatment effect estimates. Secondary numeric outcomes of pain score and opioid consumption at 48 hours and post-op day 7 will be compared via t-tests or Mann-Whitney tests as appropriate. Sleep quality during the night of surgery will be assessed via poisson regression of the count of times awakened from sleep. Subject satisfaction with the block technique will be compared using a t-test or Mann-Whitney test as appropriate.

13. Data & Safety Monitoring

In accordance with federal regulations the PI will monitor for, review, and promptly report to the IRB, appropriate institutional officials, sponsor, coordinating center and the appropriate regulatory agency head all unanticipated problems involving risks to subjects or others that occur in the course of a subject's participation in a research study (45 CFR 46.103(b)(5)(i) and 21 CFR 56.108(b)(1)), all AE reports will be reported per the DUHS IRB policies. PI will be monitoring all AEs and submitting reports to the IRB per DUHS IRB policy.

14. Privacy, Data Storage and Confidentiality

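### The count of night-time awakenings is to be analysed by Poisson regression with no provision for overdispersion, so its p-value and confidence interval may overstate the evidence

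*Combined protocol and SAP*

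**What the plan says.** Section 4 (Secondary Outcomes) lists the endpoint as "Sleep quality based on number of times awakened on the evening of POD#0". Under Postoperative Evaluation, the same section has a member of the research team collect it on the day after surgery "as a function of the number of times the patient was awoken by pain". Section 12 gives the analysis in one sentence: "Sleep quality during the night of surgery will be assessed via poisson regression of the count of times awakened from sleep".

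Nothing else in the document bears on how that model's standard error will be obtained. The other outcomes whose analysis Section 12 describes do have some provision for awkward distributions. The primary outcome has a normality check with a log transform if needed. Pain scores and later opioid use may be analysed by t-test or Mann-Whitney test, and so may satisfaction: "Subject satisfaction with the block technique will be compared using a t-test or Mann-Whitney test as appropriate".

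**The concern.** A Poisson model ties the variance of the counts to their mean. One count per patient over one night will follow that rule only if patients within an arm share much the same underlying rate of waking. If rates differ between patients, the variance exceeds the mean, and the default standard error of the log rate ratio is too small. The estimate itself is not biased by this. The p-value is too small and the interval too narrow, so a sleep benefit could be reported on evidence that does not support it.

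Some heterogeneity is plausible. Section 3 says that 25–40% of these patients have severe pain despite multimodal analgesia, and Postoperative Evaluation ties the count to waking from pain. The documents do not, however, show that awakenings are overdispersed.

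**Working it through.** **Inputs from the documents.** Two arms of 20 (Section 12: "20 patients per group (total of 40) will be required to detect a 30% difference in our primary outcome measure"), one count per patient, Poisson regression. No mean, variance or effect size is given for awakenings, so there is no stated figure for this analysis to reproduce. The sample size concerns the primary outcome only and does not enter what follows.

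**Assumptions.** Nominal two-sided 5% test, no true difference, and variance = φ × mean, with φ and the mean varied over a range. If patients' rates vary with coefficient of variation CV, then φ = 1 + mean × CV². For example, mean 2 with CV 0.5 gives 1 + 2 × 0.25 = 1.5; mean 2 with CV 1.0 gives 1 + 2 × 1 = 3.

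**Step 1: large-sample result.** The default standard error is 1/√φ of the true one, so the actual type I error is 2 × [1 − Φ(1.96/√φ)]. At φ = 2, 1.96/√2 = 1.386, giving 0.166; a 95% interval then covers about 83%.

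| φ | Default SE as share of true SE | Type I error |
|---|---|---|
| 1 | 100% | 5.0% |
| 1.25 | 89% | 8.0% |
| 1.5 | 82% | 11.0% |
| 2 | 71% | 16.6% |
| 3 | 58% | 25.8% |

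**Step 2: simulation at the trial's size.** 40,000 trials per setting, 20 per arm. Counts were Poisson at φ = 1, negative binomial above 1 and binomial at about 0.7. With arm totals S1 and S0, the default test is z = log(S1/S0)/√(1/S1 + 1/S0) against 1.96. Trials with an all-zero arm were counted as non-rejections.

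At means of 1.5 to 3, the default test's type I error was about 2% at φ = 0.7, 5% at 1, 7–8% at 1.25, 10–11% at 1.5, 16% at 2 and 25% at 3. This agrees with Step 1, and it shows that the default test is conservative if counts are less variable than Poisson.

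By between-patient CV, the default test gives:

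| Mean awakenings | CV 0.5 | CV 0.7 | CV 1.0 |
|---|---|---|---|
| 0.3 | 3.0% | 3.6% | 4.8% |
| 0.5 | 5.3% | 6.6% | 9.3% |
| 1 | 7.4% | 10.2% | 15.6% |
| 2 | 10.5% | 16.0% | 25.1% |

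**Step 3: the same trials with quasi-Poisson.** Divide z by √(Pearson X²/38) and refer it to t with 40 − 2 = 38 degrees of freedom. Type I error was 4.6–5.1% at means 1.5–3, 4.3–4.7% at mean 1 and 2.4–4.0% at mean 0.5. At mean 0.3 it was 2.0–2.4% over the CV values in the table, and 0.6–2.5% when φ is taken up to 3.

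**Step 4: price.** The interval widens relative to the default by √φ × t(0.975, 38)/1.96, which is 1.03, 1.15, 1.27, 1.46 and 1.79 for φ = 1, 1.25, 1.5, 2 and 3. If counts are truly Poisson, power falls from 51.1% to 48.7% at means 2 versus 1.2 (2.4 points), and from 43.1% to 40.5% at 1 versus 0.5 (2.6 points).

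**The case against.** The strongest reply is that this is an omission rather than an error. Poisson regression is a standard choice for a count, and robust or scaled standard errors would be compatible with the sentence as written. Harm needs two things the documents do not establish: overdispersed counts, and default errors kept without a check.

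The design may also point to the mild end. The count may cover only waking from pain, on one night. All patients have posterior capsule infiltration and a continuous adductor canal catheter. Section 5 excludes chronic pain, chronic opioid use and psychiatric disorder, which may narrow differences between patients. At a mean of 0.3 with moderate heterogeneity there is no inflation, and quasi-Poisson only makes a conservative test more so. Other remedies would also serve: robust errors gave 4.5–6.7% at means 1–3, and a negative binomial model is a further candidate. Finally, nothing in the trial turns on this p-value.

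Most of this stands as a limit on severity. It does not remove the point. If the variance method is left open, it can be chosen after the data are seen. A low mean is no guarantee either: at mean 0.3 with φ = 3, the default test rejects about 15% of the time.

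**Conclusion.** The concern holds. The plan commits a count outcome to a model whose default inference is valid only if variance equals mean (or conservative if variance is smaller), and says nothing about the alternative. The true error of a nominal 5% test could lie anywhere from about 2% to about 25% over the assumed range. The upper end needs variance three times the mean, for instance a mean of 2 with a CV of 1.0. The mechanism is certain; the size in this trial is unknown because it depends on a mean and dispersion that the documents do not give.

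The consequence is modest: one secondary outcome's p-value and interval. The change is still worth making because it is nearly free.

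**What to change.** In Section 12, specify quasi-Poisson regression for the awakening count, with the dispersion estimated from the Pearson statistic and a t reference distribution (38 degrees of freedom for the two-arm model with all 40 patients). Report the rate ratio with its 95% confidence interval.

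This takes one sentence and one software option, with no new data. The costs are the power loss of 2 to 3 points under true Poisson counts, wider intervals when counts are overdispersed (about 27% at φ = 1.5 and 46% at φ = 2, which is the correction itself), and a conservative test if mean awakenings are well below 1.

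In the same edit, reconcile the endpoint definition. Section 12 and the Secondary Outcomes list count awakenings without restriction, whereas Postoperative Evaluation counts the "number of times the patient was awoken by pain". The two could have quite different means.
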